5.2. PARTICIPANT EXCLUSION CRITERIA

An individual who meets any of the following criteria will be excluded from participation in this study:

- 1. The subject is having a concurrent Functional Endoscopic Sinus Surgery (FESS) or sinuplasty.
- 2. The subject has had rhinoplasty within the past twelve (12) months.
- 3. The subject is planning to have other concurrent rhinoplasty procedure.
- 4. The subject is planning to have other rhinoplasty procedures or will use external dilators within twelve (12) months after the index procedure.
- 5. The subject has had septoplasty and/or inferior turbinate reduction within the past six (6) months.
- 6. The subject has, in the view of the clinician, inappropriate fixation on their nasal airway.
- 7. The subject plans to have any surgical or non-surgical treatment of their nasal valve, other than the index procedure, within twelve (12) months of the study.
- 8. The subject has a permanent implant or dilator in the nasal area.
- 9. The subject has concomitant inflammatory or infectious skin conditions or unhealed wounds in the treatment area.
- 10. The subject currently has active nasal vestibulitis.
- 11. The subject has a history of nasal vasculitis.
- 12. The subject is a chronic systemic steroid or recreational intra-nasal drug user.
- 13. The subject has had a cancerous or pre-cancerous lesion and/or has had radiation exposure in the treatment area or chemotherapy.
- 14. The subject has polyps or pathology other than septal deviation and/or turbinate hypertrophy and/or lateral wall insufficiency that would contribute to airway obstruction.
- 15. The subject has a history of a significant bleeding disorder(s) that would prevent healing of the treatment area post procedure.

- 16. The subject has a known or suspected allergy to PLA or other absorbable materials.
- 17. The subject has a significant systemic disease such as poorly controlled diabetes which, in the investigator's opinion, could pre-dispose the subject to poor wound healing.
- 18. The subject is currently using nasal oxygen or CPAP.
- 19. The subject is not a candidate for procedures conducted under general anesthesia, managed anesthesia care (MAC) or conscious sedation.
- 20. For female subjects, subject is known or suspected to be pregnant or is lactating.
- 21. Any other presenting condition that in the medical opinion of the investigator would disqualify the subject.

5.3. STRATEGIES FOR RECRUITMENT AND RETENTION

A maximum of 170 subjects will be enrolled in the study to reach target of 150 subjects completing the 24 Month follow-up post-procedure. It is anticipated that this enrollment will take place in the initial 8 months of the study after study start-up. Subjects will be enrolled at approximately 25 individual sites within the United States.

Subjects will be recruited from sites' existing patient populations that are seeking treatment for nasal airway obstruction including nasal valve collapse. Anatomical considerations may impact the race distribution (e.g. some races may be less prone to lateral wall collapse), but the intention is to enroll all eligible subjects. Based on an earlier study with the device, both genders are expected to be well represented in the study.

Study brochures containing information on study participation and the Implant may be provided to the sites, as well as posters that may be displayed either as hard copies or electronically on computer monitors in the office.

The following tools will be utilized to encourage subjects' compliance to the study visit schedule:

- Subjects will receive a stipend for their time and to cover travel costs as follows: Subjects who complete the study are eligible for a total stipend of up to \$700 to be paid over a two year period. Upon completion of the Baseline, 1 Month, 3 Month, 6 Month,12 Month, 18 Month and 24 Month visits, subjects will receive a \$100 prepaid debit card at each visit or follow up. The 18 Month and 24 Month follow up evaluations will be conducted in one of the following manners: office visit, telephone interview, or completion of form by subject and mailed to office for data entry, depending on subject availability.
- Additionally, subjects will be contacted by phone, and where available automated texting and email, for both reminders to schedule or confirm upcoming study visits and as reminders for visits that have already been scheduled.

5.4. PARTICIPANT WITHDRAWAL OR TERMINATION

Participants are free to withdraw from participation in the study at any time upon request. Investigators may withdraw a subject from the study as deemed appropriate per safety measures and/or if the subject develops a medical condition that prohibits further study participation.

In the event of an early subject termination, the clinical site will document Adverse Events, Concomitant Medications changes, as appropriate, and all available data in the eCRFs. The clinical site will also complete the Study Exit eCRF.

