7.3. LOST TO FOLLOW-UP

Site personnel should make reasonable efforts to ensure that all subjects complete the requisite follow up visits. A subject will be considered lost to follow-up if the site has:

- 1. Attempted to contact the subject with a minimum of two phone calls; and
- 2. Has mailed a certified letter to the subject.

Before a subject is considered lost to follow up, the above described attempts to contact the subject must be documented in the subject's medical records and in the study CRFs.

Version 2.0 ember 7, 2017

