10.3. ANALYSES DATASETS

Three analysis populations will be considered:

- Intention-to-Treat (ITT) Population: all enrolled subjects who began a nasal Implant procedure
- Modified Intention-to-Treat (mITT) Population: all subjects enrolled who received at least one nasal Implant
- Per-Protocol (PP) 6 Month Evaluable Population: subjects with 6 month post-Implant NOSE score assessments in clinic or by telephone

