10.5. SAMPLE SIZE

The primary study hypothesis is a superiority comparison to a target proportion:

Null Hypothesis H₀: the proportion of responders at 6 months is =0.50, versus Alternative Hypothesis H_A: the proportion of responders at 6 months is \neq 0.50

See section 10.4.2 for the definition of response. This hypothesis will be evaluated using an exact test.

In order to have > 90% power to rule out a response rate \leq 50% at a 5% (2-sided) significance level, assuming a true response rate of 66%, 150 subjects with 6 month follow-up are needed. Assuming about 10% drop-out rate, up to 170 subjects will be enrolled. All mITT subjects will be used for this comparison, regardless of protocol deviations.

The assumed response rate is the minimum value expected to be consistent with previous trials, where an 80% response rate at 6 months was observed.

Sample size calculations were performed using the package RCTDesign for R version 3.2.3.

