# 2.2.1. ANALYSIS SETS FOR EFFICACY AND SAFETY

The ITT analysis set will primarily be used for safety evaluations and will include all subjects who begin the implant procedure. Subjects who are consented but do not begin the implant procedure will not be included in the ITT analysis set. Because this is a singlearm, open-label study, the exclusion of subjects who do not begin the implant procedure is unlikely to result in biased response estimates. Subjects who begin the implant procedure but do not successfully receive an implant will be included in the ITT analysis set.

The mITT analysis set will consist of all subjects who successfully receive at least 1 Spirox LateraTM implant. Analyses supporting the primary and major secondary endpoints will, to the extent possible, be based on the mITT analysis set. Safety evaluations for events within 7 days of the implant procedure will be based on the ITT analysis set, and cumulative adverse events at 6 months will be based on the mITT analysis set. An important subgroup of the mITT analysis set is the 6 Month Evaluable (6ME) Set, which includes subjects with 6 month post-implant NOSE score assessments in clinic or by telephone.

The per-protocol (PP) analysis set will consist of all mITT subjects who have no major protocol deviations or events that might impact NOSE scores. These deviations may include changes to background nasal medications, prohibited medications and additional procedures prohibited by the protocol.

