### 4.2.2. ANALYSIS METHODS

The primary efficacy endpoint of 6 month response proportion will be assessed using a 2sided exact test to determine whether the proportion of responders is significantly different than 0.5. Only subjects in the 6ME set will be included in the primary endpoint analysis. The corresponding exact (Clopper-Pearson) 2-sided 95% confidence interval will be calculated. The null hypothesis that the proportion of responders is = 0.5 will be rejected if the p-value is < 0.05.

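### No rule secures a 6-month NOSE score from implanted subjects who are withdrawn or declared lost early, and the primary test then leaves them out

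*Protocol*

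**What the plan says.** **Investigator withdrawal (Protocol 5.4).** "Investigators may withdraw a subject from the study as deemed appropriate per safety measures and/or if the subject develops a medical condition"; the sentence goes on to limit the medical condition to one that prohibits further participation. The two grounds are joined by and/or, so that limit does not attach to the safety ground. Lack of effect is not listed as a ground. When a subject leaves early, "the clinical site will document Adverse Events, Concomitant Medications changes, as appropriate, and all available data in the eCRFs", together with the exit form.

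**Lost to follow-up (Protocol 7.3).** Two conditions must both be met and documented: "Attempted to contact the subject with a minimum of two phone calls" and "Has mailed a certified letter to the subject". No visit or time point is named, and no new attempt is required when month 6 falls due.

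**Schedule (Protocol 7.7 and 7.8).** The Early Exit column holds the adverse event assessment and the exit form, but no NOSE scale. Section 7.8 sets adverse events and medication changes as the minimum.

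**Primary analysis.** SAP 4.2.2: "Only subjects in the 6ME set will be included in the primary endpoint analysis". SAP 2.2.1 defines that set as one "which includes subjects with 6 month post-implant NOSE score assessments in clinic or by telephone", and Protocol 10.3 has the same definition. Protocol 10.4.2 also tests the primary hypothesis in this population. Protocol 10.5 says otherwise: "All mITT subjects will be used for this comparison, regardless of protocol deviations".

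**Missing data.** Protocol 10.4.2 commits to sensitivity analyses and gives LOCF and missing-as-non-responder as possible methods. SAP 4.2.2.1 names the same two but words the imputation as optional.

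**The concern.** The implant is placed once. After that, follow-up consists of questionnaires, examinations, imaging and adverse event enquiry, so there is no continuing study treatment to stop. Ending participation at that stage mainly ends data collection, and the safety ground for doing so is left to the judgement of an investigator in an open-label study. Section 7.3 likewise allows a subject who cannot be reached early on to be classed as lost, with nothing that prompts a further attempt at the visit that carries the primary endpoint.

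Because the primary test conditions on having a 6-month score, both routes remove subjects from its numerator and denominator. If those who leave do worse than those who stay, the reported response rate is too high. Safety data are touched as well. Protocol 8.1 collects serious events and device effects to the end of the subject's participation, so new events after a withdrawal would not be captured for the 6-month primary safety endpoint. Events already known are still followed (Protocol 8.3).

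**Working it through.** **Inputs.** Null proportion 0.50, two-sided alpha 0.05, exact test (SAP 4.1.1 and 4.2.2). Assumed true rate 66% with 150 evaluable, about 10% drop-out and up to 170 enrolled (Protocol 10.5). The SAP sample size section has 120 evaluable, 20% drop-out and 150 to 170 enrolled. The documents give no figure for how many exits before month 6 would be non-responders; that share is an assumption, varied below.

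**1. The plan's own power figure.** Find the smallest count r with two-sided exact p<0.05, then P(X ≥ r) at 0.66.
- n=150: r=88, power 97.5%.
- n=120: r=72, power 93.0%.

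Both agree with the stated power of more than 90%.

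**2. Effect on the reported rate.** With R responders among N treated and m non-responders lost, the reported rate is R/(N − m).
- m=0: 99/150 = 66.0%
- m=5: 99/145 = 68.3%
- m=10: 99/140 = 70.7%

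**3. Effect on the test near the boundary** (exact two-sided p against 0.5).
- 86/150 = 57.3%, p=0.086
- 86/147 = 58.5%, p=0.047
- 86/145 = 59.3%, p=0.030

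With 150 treated and 5 non-responders lost, only 85, 86 or 87 responders change the result. At 84 the test still fails (84/145, p=0.067), and at 88 it already passes without any loss (88/150, p=0.041). The probability of 85 to 87 responders out of 150 is 1.8% at a true rate of 66% and effectively zero at 80%.

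**4. Effect on false positives.** With a true rate of 50% and 150 treated, the chance of wrongly concluding superiority is P(X ≥ 88) = 2.0% with no loss. It is P(X ≥ 85) = 6.0% if 5 non-responders are lost (threshold for n=145) and P(X ≥ 83) = 11.0% if 10 are lost (threshold for n=140).

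**5. At the planned drop-out.** Rate among those observed = (N × p − responders lost)/n, with p=0.50.

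| Lost | Share of failures among the lost | Observed rate | Chance of a false superior result |
|---|---|---|---|
| 20 of 170 | 50% | (85 − 10)/150 = 50.0% | 2.0% |
| 20 of 170 | 75% | (85 − 5)/150 = 53.3% | 11.0% |
| 20 of 170 | 100% | 85/150 = 56.7% | 34.1% |
| 30 of 150 | 50% | (75 − 15)/120 = 50.0% | 1.8% |
| 30 of 150 | 75% | (75 − 7.5)/120 = 56.3% | 23.1% |
| 30 of 150 | 100% | 75/120 = 62.5% | 74.7% |

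The 50% rows show that loss unrelated to outcome does not bias the rate. The 100% rows are the extreme. They also assign the whole drop-out allowance to exits of this kind, although the allowance covers all causes.

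**6. Robustness at the design rate.** Start from 99 responders among 150 observed and add lost subjects as failures. With 21 added, 99/171 gives p=0.046; with 22, 99/172 gives p=0.056. The result therefore survives up to 21 lost failures. At 80% (120/150) it survives 60.

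**7. Prior experience.** In the Protocol 2.2 table the prior study has N=29 at 3 months and N=30 at 6 months, with 30 treated. So 0 of 30 were missing at month 6 (exact 95% CI 0 to 11.6%), and the one subject without a 3-month score did give one at month 6.

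**The case against.** A reader might infer that likely failures will leave before month 6 and disappear from the results. The documents do not support that. Lack of effect is not a withdrawal ground, and the medical ground is confined to conditions that prohibit participation. A subject withdrawn for a safety event may well be a responder. In the prior study every subject has a 6-month score despite three implant retrievals, and the three exits for other nasal surgery came after month 12. Those exits show that leaving can follow further nasal surgery, but not that it happens before the primary endpoint.

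Nor would such subjects go unreported. Missing-as-non-responder is a named sensitivity analysis, and in the boundary example it would restore 86/150 and expose the difference. Protocol 10.4.5 compares baseline features by whether the 6-month score is available, SAP 3.3 counts discontinuations before 6 months, Protocol 11 requires the reason for withdrawal, and adverse events are recorded at exit. Two calls is a minimum, a certified letter is also required, and Protocol 5.3 adds reminders and a payment per visit. The boundary example is also a narrow case, as steps 3 and 6 show.

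All of this stands, and it limits the point to a possible bias. It does not remove the gap. The SAP makes the imputation optional, a comparison of baseline features says nothing about outcome, and no analysis recovers a score that was never sought. A telephone score is accepted for month 6 in Protocol 10.3, but 5.3 sets out remote collection only for months 18 and 24.

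**Conclusion.** The point holds as a cheap improvement. Protocol 5.4, 7.3 and 7.7 together allow an implanted subject to leave before month 6 with no further attempt at a NOSE score, and the primary test then omits that subject. If such exits are related to poor outcome, the response rate is biased upward.

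If all those lost are non-responders, a 66.0% rate is reported as 68.3% with 5 lost of 150, or 70.7% with 10 lost. Under a true rate of 50%, the same losses raise the chance of a false conclusion from 2.0% to 6.0% or 11.0%. At the planned 66% rate the conclusion is hardly at risk; what may be overstated is the estimate. The number lost and their outcomes are assumptions, and if the lost resemble the rest there is no bias.

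The conflict over the primary set between Protocol 10.5 and Protocol 10.4.2 with SAP 4.2.2 needs reconciling in any case. That settles how missing scores are counted but does not collect them.

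**What to change.** - **Protocol 5.4:** state that investigator withdrawal after the index procedure does not by itself end NOSE and adverse event follow-up. A 6-month NOSE score is still sought, by telephone if needed (already accepted in 10.3), unless the subject withdraws consent, dies or cannot respond.
- **Protocol 7.3:** for any subject who missed an earlier visit, require renewed contact attempts within the 6-month window before the 6-month score is treated as missing.
- **Protocol 7.7:** add the NOSE scale to the Early Exit column.

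An outright ban on investigator withdrawal, or holding back lost status until month 24, would go further than needed. The subject's right to withdraw is unchanged.

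Cost: protocol wording, a few extra calls and slightly more site effort.

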5.5. PREMATURE TERMINATION OR SUSPENSION OF STUDY

The study enrollment may be temporarily suspended or prematurely terminated if there is sufficient reasonable cause. Written notification, documenting the reason for study suspension or termination, will be provided by the suspending or terminating party to the investigator and regulatory authorities. If the study is prematurely terminated or suspended, the site PI will promptly inform the IRB(s) and will provide the reason(s) for the termination or suspension.

Both the sponsor and the investigator reserve the right to terminate the study at any time. In terminating the study, the sponsor and the investigator will assure that adequate consideration is given to the protection of the Subjects interests.

If the sponsor, investigator, study monitor, or appropriate regulatory officials discover any conditions arising during the study that indicate that the study enrollment should be suspended or that the study site should be terminated, this action may be taken after appropriate consultation among the sponsor, investigator, and study monitor. Conditions that may warrant enrollment suspension or termination of the study site or of the study itself, may include, but are not limited to, the following:

- The discovery of an unexpected, serious, or unacceptable risk to the subjects enrolled in the study;
- A decision on the part of the sponsor to discontinue the study;
- A decision on the part of the sponsor to suspend or discontinue evaluation of the device;
- A request from a regulatory authority;
- Failure of the investigator to enroll subjects into the study at an acceptable rate;
- Failure of the investigator to comply with pertinent regulations of appropriate regulatory authorities;
- Submission of knowingly false information from the research facility to the sponsor, study monitor, or appropriate regulatory authority;
- Insufficient adherence to protocol requirements.
- Determination that it is unlikely that the study null hypothesis can be rejected

In the event of enrollment suspension, the study may resume once concerns about safety, protocol compliance, or data quality are addressed to the satisfaction of the sponsor, IRB and/or FDA.

Subjects that have been enrolled and have undergone the index procedure at the time of study enrollment suspension will only be followed per the study schedule through the 24-Month close-out visit in the event the study is re-started. Subjects that have been consented, but not yet undergone index procedure, will be delayed until a determination to restart enrollment has been made. These latter subjects will be re-consented if the enrollment suspension lasts longer than thirty (30) days.

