7.1.4. Follow-Up Evaluation Visits (Visit 4-9)

Safety and performance data will be collected at 1 month (+/- 7 days), 3 months (+/-15 days), 6 months (+/- 15 days) 12 months (+/- 30 days), 18 months (+/- 30 days) and 24 months (+/- 30 days) post procedure.

A detailed description of the visit assessments and evaluations are located in Section 7.2. The following data will be collected:

- 1. NOSE scale (See Section 7.2.1)
- 2. NAO Breathing Assessment (See Section 7.2.2)
- 3. Subject Satisfaction Questionnaire (See Section 7.2.13)*
- 4. Post Procedure Health Economics Questionnaire (See Section 7.2.4)*
- 5. Update Concomitant Medications, if changed (See Section 8.9)
- 6. Adverse Events since last visit (See Section 8)
- 7. Post Procedure Nasal Exam (see section 7.2.7)*
- 8. Lateral Wall Motion Video 6 Month Visit only (See Section 7.2.9)*
- 9. Photography Cosmetic (select sites only) 3 and 6 Month Visits only (See Section 7.2.10)*
- 10. Photography 3D (select sites only) 3, 6 and 12Month Visits only (See Section 7.2.11)*

*This assessment/evaluation will not be collected at the 18 month and 24 month follow ups

Spirox Latera™ implant support of lateral wall cartilage (LATERAL-OR) study	Version 2.0
SPI-CP-301	September 7, 2017

Adverse events observed through the 12 month visit will be collected and documented. Only adverse device effects will be collected beyond the 12 month visit. Spirox will be notified as necessary pursuant to the description provided in Section 8. Data collected for these visits should be entered into the EDC no later than seven (7) days after the completion of each visit.

Upon completion of the follow-up visit activities, the subject will be scheduled for the next Follow-up Evaluation Visit.

Subject participation will be complete at the 24 month follow-up time point and documented in the Study Exit eCRF.

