7.7. STUDY SCHEDULE OF EVENTS TABLE

Study Events	Screening & Enrollment (Visit 1)	Baseline Evaluation (Visit 2) ¹	Treatment (Visit 3)	Follow Up 1 mo (Visit 4)	Follow Up 3 mo (Visit 5)	Follow Up 6 mo (Visit 6)	Follow Up 12 moStudy Visit (Visit 7)	Follow Up 18 & 24 mo/Final Study Visit (Visits 8 & 9)	Early Exit
Secure Informed Consent	Х								
Secure Re-Consent for 18M and 24M Follow Up							Х		
Inclusion/Exclusion	Х		X ²						
NOSE Scale (PRO) ³	Х	Х	X ²	Х	Х	Х	Х	Х	
NAO Breathing Assessment (PRO)		Х		Х	Х	Х	Х	Х	
Subject Satisfaction Questionnaire (PRO)				Х	Х	Х	Х		
Health Economics Questionnaire (PRO)		Х		Х	Х	Х	Х		
Nasal Medical History/Nasal Geometry		Х							
Nasal Exam		Х		Х	Х	Х	Х		
Lateral Wall Motion Video		Х				Х			
Photography- 3D Camera (select sites)		Х			Х	Х	Х		
Photography –Cosmetic (select sites)		Х			Х	Х			
Turbinate Hypertrophy Contribution to		Х							
NAO assessment (Nasal Decongestant)									
Photography – Planning Images			Х						
NAO Treatment			Х						
Concomitant Medications		Х	Х	Х	Х	Х	Х		
Adverse Event Assessment			X	X	X	X	Х		Х
Adverse Device Effects Assessment								X	
Complete Study Exit Form								X ⁴	Х

¹ Visit 2 activities may be done in conjunction with Study Visit 1. In this instance, the Screening NOSE Scale is not required.

² If Visit 3 (Treatment Visit) is more than 1 month after Visit 1, inclusion/exclusion criteria need to be re-confirmed. Additionally, subjects should be asked to review IC form, initial and date the IC document to confirm continued consent for participation, and complete NOSE scale.

³ If Visits 1, 2 and 3 are done on the same day, the Screening and Treatment NOSE Scales are not required.

⁴To be completed at 24M follow up.

Spirox Latera™ implant support of lateral wall cartilage (LATERAL-OR) study	
SPI-CP-301	Sep

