8. ASSESSMENT OF SAFETY

8.1. SPECIFICATION OF SAFETY PARAMETERS

All Serious Adverse Events (SAE), Adverse Device Effect (ADE) and Serious Adverse Device Effects (SADE) will be collected and documented through the end of subject participation in the study. In addition, all non-serious device and procedure-related Adverse Events (AE) and all non-serious head and neck, and/or respiratory related AEs will also be collected and documented.

The primary safety endpoint evaluation will consider nasal procedure related and Latera related adverse events through 6 months post-procedure.

The following information for each AE, ADE, SAE and SADE will be collected:

- Date of onset
- Status and/or Outcome
- Date of resolution
- Adverse Event/Effect type
- SAE or SADE
- Severity of event
- Relation to Study Device and/or procedure
- Action taken
- Descriptive narration of Event/Effect

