8.3. TIME PERIOD AND FREQUENCY FOR EVENT ASSESSMENT AND FOLLOW-UP

The occurrence of an AE or SAE may come to the attention of study personnel during study visits and interviews of a subject presenting for medical care, or upon review by a study monitor.

All device or procedure-related AEs, including local and systemic reactions not meeting the criteria for SAEs, will be captured on the appropriate CRF. Information to be collected includes event description, time of onset, clinician's assessment of severity, relationship to study product (assessed only by those with the training and authority to make a diagnosis) or concomitant procedures, and time of resolution/stabilization of the event. All AEs occurring while on study must be documented appropriately regardless of relationship. All AEs will be followed to adequate resolution.

Any medical condition that is present at the time of the participant's procedure will be considered as a baseline condition or comorbidity, and will not reported as an AE. However, if the subject's condition deteriorates at any time during the study, and the condition is procedure/device related, it will be recorded as an AE. AEs will be recorded in the data collection system throughout the study.

Changes in the severity of an AE will be documented. AEs characterized as intermittent require documentation of onset and duration of each episode.

At each study visit, the investigator will inquire about the occurrence of AE/SAEs since the last visit. Events will be followed for outcome information until resolution or stabilization.

8.4. **REPORTING PROCEDURES**

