10.4.4. SAFETY ANALYSES

Two analysis sets will be used to *summarize* adverse events. The ITT analysis set will be used to summarize acute adverse events (through 1 month post procedure), and the mITT analysis set will be used to summarize adverse events over the entire duration of follow-up. The primary safety reporting time-point is 6 months post-implant.

The overall incidence (i.e., number and percent of subjects with 1 or more adverse event in each class) of adverse events, serious adverse device events, serious adverse events, fatal adverse events, and device related events (e.g., possibly, probably or definitely related) will be calculated for the acute phase, through 6 months post-procedure and for the entire duration of follow-up. The overall incidence of mild, moderate and severe events will be calculated by considering the most severe event for each subject.

In addition, the overall incidence for each adverse event type will be calculated. The adverse event types will be classified according to the following categories:

- Excessive Inflammation
- Significant Foreign body sensation
- Excessive Pain or discomfort
- Infection
- Implant Extrusion, defined as body rejection of implants
- Implant Retrievals, defined as surgeon or subject initiated removal of implants not associated with body rejection of implant
- Implant bent or fractured
- Implant loose
- Implant migration
- Skin irritation
- Hematoma
- Unintended perforation of the skin
- Other

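### Protocol 5.5 ties scheduled follow-up of already-implanted subjects to a restart after an enrollment suspension, a condition that 7.1.4 and the Protocol Summary do not carry

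*Protocol*

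**What the plan says.** Protocol 5.5 deals with suspension of enrollment. Subjects who have had the index procedure by then "will only be followed per the study schedule through the 24-Month close-out visit in the event the study is re-started". No other sentence says which visits these subjects have during a hold, or if no restart follows. Among the listed grounds for suspension or termination is "The discovery of an unexpected, serious, or unacceptable risk to the subjects enrolled in the study".

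The general schedule carries no such condition. Section 7.1.4 sets visits at 1, 3, 6, 12, 18 and 24 months and adds: "Subject participation will be complete at the 24 month follow-up time point and documented in the Study Exit eCRF". The Protocol Summary also gives a participant duration of 24 months. The one gate in the schedule of events (7.7) is a consent step at 12 months, "Secure Re-Consent for 18M and 24M Follow Up".

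On safety, 8.3 states: "At each study visit, the investigator will inquire about the occurrence of AE/SAEs since the last visit". Section 8.1 says that serious events and device effects "will be collected and documented through the end of subject participation in the study". Section 10.4.4 adds: "The primary safety reporting time-point is 6 months post-implant".

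**The concern.** What is suspended is enrollment, but the consequence falls on people who already carry the implant. Active inquiry about adverse events is tied to study visits, so if visits pause, scheduled asking pauses too. A safety signal is one of the reasons for a hold, so the rule can apply just when seeing treated subjects is most useful. Events that subjects do not raise themselves would then be found later or, without a restart, possibly not through the study at all.

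The 6-month visit matters most. It is the primary safety reporting time-point and the primary efficacy visit, and the next scheduled visit is at 12 months.

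**Working it through.** **Reading the text**

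| Situation | What 5.5 gives treated subjects | What remains elsewhere |
|---|---|---|
| Hold, no restart | No scheduled visits, read literally | Early-termination documentation (5.4, 7.8, Early Exit column of 7.7); follow-up of known events (8.3, 8.4.2) |
| Hold, then restart | The schedule through 24 months; unclear whether visits falling due in the hold take place | The same follow-up of known events; the next visit asks back to the last one (8.3) |
| No hold | 5.5 does not apply | Full schedule in 7.1.4 |

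**Gap between adverse event inquiries if a visit is skipped and not made up**

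- 6-month visit: 12 − 3 = 9 months, instead of 6 − 3 = 3.
- 3-month visit: 6 − 1 = 5 months, instead of 3 − 1 = 2.

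**The plan's own power claim, reproduced.** Two-sided exact binomial test of 0.50 at 5%, true response rate 0.66. With 150 subjects (Protocol 10.5) the test rejects in favour of the device at 88 or more responders; power is 97.5%. With 120 (SAP, Sample Size Justification) it rejects at 72 or more; power is 93.0%. Both agree with the stated figure of more than 90%.

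**How many 6-month windows a hold could close**

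Inputs: 170 subjects over 8 months (Protocol 5.3); 6-month window of ±15 days (7.1.4), taken as 1 month wide.

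Assumptions: even accrual, treatment at enrollment, no visits during the hold, enrollment resuming afterwards to 170.

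- Accrual: 170 / 8 = 21.25 per month.
- A subject treated at month t has a 6-month window from t + 5.5 to t + 6.5.
- For a hold from month S to S + H, the window lies wholly inside if t is between S − 5.5 (or 0, if later) and S + H − 6.5. The count is 21.25 times the length of that interval.

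| Hold starts at month | H = 1 | H = 2 | H = 3 |
|---|---|---|---|
| 1, 2 or 3 | 0 | 0 | 0 |
| 4 | 0 | 0 | 10.6 |
| 5 | 0 | 10.6 | 31.9 |
| 6, 7 or 8 | 0 | 21.25 | 42.5 |

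For example, S = 4 and H = 3 gives t from 0 to 0.5, so 0.5 × 21.25 = 10.6. S = 6 and H = 3 gives t from 0.5 to 2.5, so 2 × 21.25 = 42.5.

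**Power if every one of those visits were skipped altogether**, with 10% drop-out applied once:

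- No windows lost: 170 × 0.9 = 153; power 97.4%.
- 21.25 lost: (170 − 21.25) × 0.9 = 133.9, about 134; power 96.4%.
- 42.5 lost: (170 − 42.5) × 0.9 = 114.75, about 115; power 92.6%.

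Power falls below 90% only under a harsher assumption: that every subject whose 6-month target date falls in a 3-month hold is skipped, although part of the window may be open. That is 3 × 21.25 = 63.75 subjects for a start at months 6 to 8. It leaves (170 − 63.75) × 0.9 = 95.6, about 96; power 85.2%.

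**No restart, hold at month 6.** About 6 × 21.25 = 127.5 subjects would have been treated. At most 0.5 × 21.25 = 10.6 could have had an early 6-month visit, so about 117 to 128 would have none.

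**The case against.** The sentence may be a drafting slip, meant to say that treated subjects carry on while enrollment is held. It does not forbid visits during a hold, and a schedule kept through month 24 can include them. That stands for a hold that later ends: delay is possible there, not certain. It does not help without a restart, where the text gives no scheduled follow-up.

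A reader might infer that safety reporting stops, or that 5.5 contradicts 8.1 and 8.3. The documents do not support that. Known events are followed to resolution or stabilization, and serious events are still reported (8.3, 8.4.2). Events may also surface when a subject seeks care or through monitor review (8.3). The Medical Monitor and Scientific Advisory Board review reported serious events (8.6). Early termination requires documentation of adverse events and a study exit form (5.4, 7.8). On termination, "In terminating the study, the sponsor and the investigator will assure that adequate consideration is given to the protection of the Subjects interests". These are real safeguards, but none provides a scheduled visit.

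A reader might also equate a closed visit window with loss from the primary analysis. The 6-month evaluable set needs a 6-month NOSE score, in clinic or by telephone, and its definition has no ±15-day condition (Protocol 10.3, SAP 2.2.1). An out-of-window visit removes a subject from the SAP's per-protocol set (SAP 3.6). A late score could therefore still count.

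Finally, a suspension may never happen, several listed grounds have nothing to do with safety, and the device is cleared and used on label. This limits the weight of the point but does not make the sentence right.

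**Conclusion.** The point holds in a limited form. As written, 5.5 makes scheduled follow-up of treated subjects depend on a restart, while the rest of the protocol does not. Without a restart, scheduled visits and visit-based inquiry end; with one, they may be delayed. Known events are still reported and followed in either case.

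The size is contingent. Under even accrual, holds of 1 to 3 months close between 0 and about 42 six-month windows: none for starts at months 1 to 3, and the maximum for a 3-month hold starting at months 6 to 8. If the study restarts and reaches 170, power stays above 90% even if all of those visits are lost. It would be wrong to conclude that the primary test is underpowered; the issue is safety follow-up of treated subjects. The probability and length of a hold are not in the documents. This is a cheap improvement, not a flaw in the primary analysis.

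**What to change.** Replace the sentence in Protocol 5.5 on subjects who have had the index procedure with:

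> *Subjects who have undergone the index procedure will continue scheduled visits and AE/ADE collection per 7.1.4 during any enrollment suspension, whether or not enrollment restarts, subject to continuing consent (including the 12-month re-consent) and any IRB or regulatory restriction; if the study is terminated, the existing early-termination provisions (5.4, 7.8) apply.*

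The cost is one amended sentence, plus carrying on visits during a hold that are already planned. No new procedure and no SAP change is needed.
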